The Cardiovascular Inflammation Reduction Trial (CIRT) is an NHLBI funded multicenter clinical trial (U01 HL 101422) that will randomly allocate 7,000 patients with stable CAD and either type 2 DM or metabolic syndrome to low-dose methotrexate (LDM; target dose 15 to 20 mg per week) plus usual care, or placebo plus usual care over a follow-up period of 2 to 4 years (average 3 years). CIRT is an event-driven trial such that in the absence of extreme effects, the trial will conclude after accrual of at least 530 primary endpoints, estimated to provide 90% power to detect a 25% relative risk reduction. The CIRT primary endpoint is a composite of nonfatal myocardial infarction (MI), stroke, and cardiovascular death. Secondary endpoints include total mortality, coronary revascularization, unstable angina requiring unplanned revascularization, and hospitalization for heart failure, with additional pre-specified endpoints such as incident venous thrombosis, atrial fibrillation, peripheral artery disease, and severe aortic stenosis. In addition, effects on measures of quality of life will be assessed using the standardized SF-36 Health Survey. Participants will be recruited from roughly 400 clinical sites in the United States and Canada.

In addition to LDM or matching placebo, all study participants (including those on placebo) will receive folic acid 1.0 mg 6 days per week, a therapy known to reduce side effects that can be associated with LDM. To further ensure safety and improve long-term compliance, the trial design incorporates a 5- to 6-week open-label, active-therapy run-in (maximum 8 weeks) for all potentially eligible participants so that those unable to initially tolerate LDM are excluded prior to randomization. Additional details of the CIRT parent trial are included in the appended CIRT IRB application, approved on 6/13/2012 (Appendix).

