## II. SPECIFIC AIMS

Coronary flow reserve (CFR, calculated as the ratio of hyperemic over rest myocardial blood flow) is emerging as a powerful quantitative prognostic imaging marker of clinical cardiovascular risk. CFR provides a robust and reproducible clinical measure of the integrated hemodynamic effects of epicardial CAD, diffuse atherosclerosis, and microvascular dysfunction on myocardial tissue perfusion. Inflammation is a key mediator of this constellation of abnormalities, affecting the entire coronary vasculature, but no clinical trial to date has shown that directly reducing inflammation lowers cardiovascular event rates. As such, the recently launched Cardiovascular Inflammation Reduction Trial (CIRT) provides a unique opportunity for mechanistic investigation of the impact of anti-inflammatory therapy on changes in CFR as a reflection of coronary vascular dysfunction, which may precede clinical outcomes, particularly in patients at high-risk of events. We are ideally positioned to examine the impact of inflammation on CFR, having extensive experience in both the quantitation of CFR using clinically-integrated dynamic positron emission tomography (PET) and the ability to assess its association with cardiovascular outcomes.

The *central hypothesis* of this ancillary proposal, CIRT-CFR, is that reducing systemic inflammation using low-dose methotrexate (LDM) will, compared to placebo, quantitatively improve myocardial blood flow and coronary flow reserve as measured by PET over 1-12 months, in stable CAD patients with type 2 diabetes or metabolic syndrome enrolled in CIRT. In so doing, improvement in coronary vasoreactivity, endothelial function, and tissue perfusion may have beneficial effects on myocardial mechanics, left ventricular deformation and function and, ultimately, symptoms and prognosis.

**AIM 1.** To test the hypothesis that systemic inflammation is a critical determinant of coronary flow reserve and myocardial tissue perfusion, as assessed by quantitative PET imaging, in stable CAD patients with type 2 diabetes or metabolic syndrome. Specifically, we propose that treatment with LDM at a target dose of 15 to 20 mg orally weekly for 1-12 months will, compared to placebo, result in:

**Hypothesis #1:** Improved global coronary flow reserve in response to dipyridamole, reflecting primarily endothelium-independent vasodilation.

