#### **Inclusion criteria:**

- a. Age  $\geq 18$  years at screening;
- b. Documented past history of MI OR past evidence of multivessel CAD by angiography, completed any planned coronary revascularization associated with a qualifying event at least 60 days prior to enrollment, and clinically stable for  $\geq 60$  days prior to enrollment; qualifying prior MI must be documented either by hospital records, evidence on current ECG of Q waves in 2 contiguous leads, and/or an imaging test demonstrating wall motion abnormality or scar; qualifying evidence of multivessel CAD by angiography must be documented by CAD in at least two major epicardial vessels defined either as the presence of a stent, a coronary artery bypass graft, or an angiographic lesion of 60% or greater (left main CAD that has been revascularized with a stent or bypass graft will qualify as multivessel disease, as will the presence of a 50% or greater isolated left main stenosis);
- c. History of type 2 DM or metabolic syndrome (meeting 2004 AHA/NHLBI definition\*) at time of study enrollment; \*includes any 3 of the following 5 diagnostic criteria: waist circumference  $\geq 102$  cm in men or 88 cm in women; triglycerides  $\geq 150$  mg/dl or on drug treatment for elevated triglycerides; high-density lipoprotein cholesterol (HDL-C)  $< 40$  mg/dL in men or  $< 50$  mg/dL in women or on drug treatment for reduced HDL-C; systolic blood pressure  $\geq 130$  mm Hg or diastolic blood pressure  $\geq 85$  mm Hg or on drug treatment for hypertension; and elevated fasting glucose  $\geq 100$  mg/dL or on drug treatment for elevated glucose.
- d. Willingness to participate as evidenced by signing the CIRT and CIRT-CFR informed consent.

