**Positron Emission Tomography (PET):** Regional and global myocardial blood flow (MBF) will be assessed using PET imaging in accordance with the study-specific acquisition protocol. The investigative teams at BWH, OHI, and UAB have extensive experience in performing these procedures, and quantifying myocardial blood flow. PET scans will be performed using a whole body PET/CT scanner. Anti-hypertensives and beta-blockers will be withheld on the morning of the study. Patients will be allowed to continue using sublingual nitroglycerin as needed. Studies will be performed after 4 hours of fasting and 24 hours of abstinence from caffeine. The visit will take approximately 5 hours, including patient preparation. MBF will be measured at rest and during dipyridamole, adenosine, or regadenoson infusion, using N-ammonia or Rubidium, as the flow tracer. Importantly, the same radiopharmaceutical should always be used for the baseline and follow-up scans. After transmission imaging and beginning with the intravenous (IV) bolus administration of N-ammonia (~10-20 mCi, adjusted based on whether 2D- or 3D-imaging is used) or Rubidium (~10-20 mCi for 3D imaging), list mode images will be acquired for 20 or 7 minutes, respectively. Thirty (N-ammonia) or 10 (Rubidium) minutes later, patients will undergo a standard infusion of dipyridamole (0.56 mg/kg over 4 minutes), adenosine (0.14 mg/kg/min for 4 minutes), or regadenoson (0.4 mg bolus over 10 seconds). At peak hyperemia, a second dose of N-ammonia (~10-20 mCi, adjusted based on whether 2D- or 3D-imaging is used) or Rubidium (~10-20 mCi for 3D-, and 30-50 mCi for 2D imaging) will be injected IV, and images recorded in the same manner. The heart rate, blood pressure, and 12-lead ECG will be recorded at baseline and throughout the infusion of dipyridamole, and at recovery. All studies will be reviewed at the sites by site investigators for clinically important findings. All PET scans will be done for research (non-clinical) purposes only. For safety reasons, all studies will be reviewed at the sites by site investigators for clinically important findings. No reports or analyses will be provided to sites from the PET core laboratory and studies will not be assessed in real-time.

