**Two-dimensional echocardiography:** Echocardiograms will be performed by site sonographers trained and certified by the echo core laboratory in the study-specific acquisition protocol. The noninvasive core laboratory at BWH has extensive experience in quantitative echocardiography in the context of therapeutic clinical trials. [name] also directs the core laboratory in the analysis of echocardiographic images in the NIH-funded ARIC study. Images will be acquired as recommended by the American Society of Echocardiography (ASE) and in a manner consistent

with standard practices for patient comfort and position. In addition, the echo protocol includes specific views to ensure optimal imaging for specific views to: (1) assess LV diastolic function, and (2) ensure optimal imaging for off-line LV deformation analysis with speckle-tracking software (i.e., images of the LV will be captured at high frame rates of 50-70 fps). The protocol will take approximately 35 minutes, including patient preparation. A superset of a standard echo exam will be performed, emphasizing endocardial border optimization and on-axis imaging. All studies will be acquired and stored in digital DICOM format, with CD/DVD copy for site backup. All studies will be reviewed at the sites by site investigators for clinically important findings. All echos will be done for research (non-clinical) purposes only. No reports or analyses will be provided to the sites from the echo core laboratory and studies will not be assessed in real-time.

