**Exploratory analyses:** The proposed ancillary study will not be powered to detect changes in clinical outcomes, patient symptoms, or changes in circulating biomarkers. However, we recognize the importance of exploring the correlations between the changes in CFR and LV function over the 1-12-month observation period and these meaningful outcomes. We propose the following exploratory tertiary objectives: (1) Explore an interaction between the change in CFR at 1-12 months with composite MACE that includes cardiac and all-cause mortality, recurrent MI, stroke, coronary revascularization, and hospitalization for unstable angina requiring unplanned revascularization or for congestive heart failure, occurring 3-4 years after randomization. We will use a proportional hazards model to explore relationships of CFR and its change with time until development of the first clinical event occurring through the end of randomization. We recognize that this exploratory analysis, in particular, will be limited because we expect only ~25 composite events in total in our study sample. (2) Correlate the change in CFR at 1-12 months with the corresponding change in QOL scores, as assessed by the standardized SF-36 Health Survey to be administered during enrollment, 12-month, and final study visits of the parent CIRT trial. Prior assessments with this tool have shown significant differences in baseline and 6-month follow-up scores in a modest-sized (n=120) patient population post-MI. (3) Correlate the change in CFR and LV function with the corresponding changes in circulating biomarkers of inflammation (hsCRP, IL-1) and myocardial strain (NTproBNP, hsTroponin), as assessed from stored biorepository samples at 8, 12 and 24 months after randomization. Analyses of changes in QOL scores and biomarkers will use linear regression models, after transforming changes to normality as necessary, and with control for baseline trial stratification variables, baseline QOL scores and biomarker levels, and treatment assignment. Main independent variables will be baseline and 1-12-month change in CFR. (4) Assess correlations among the baseline PET, echo, biomarker, and SF-36 data using linear regression models, as described above for continuous variables.

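### The exploratory CFR–MACE model counts any coronary revascularization, including one that a site-reviewed study scan might prompt, and counts MI only if recurrent: a minor point with a cheap fix

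*Combined protocol and SAP*

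**What the plan says.** **Scan review.** The PET paragraph of section V (Study Procedures) states: "For safety reasons, all studies will be reviewed at the sites by site investigators for clinically important findings". The echocardiography paragraph has the same rule: "All studies will be reviewed at the sites by site investigators for clinically important findings". The PET paragraph also limits the use of the scans: "All PET scans will be done for research (non-clinical) purposes only", and "No reports or analyses will be provided to sites from the PET core laboratory and studies will not be assessed in real-time". Neither paragraph says what happens to a finding from the site's own review: who is told, whether it is recorded, or how a resulting procedure is treated in the analysis.

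**Outcome.** Section VI, Exploratory analyses, objective (1), fits a proportional hazards model of CFR and its change on time to the first event in a "composite MACE that includes cardiac and all-cause mortality, recurrent MI, stroke, coronary revascularization, and hospitalization for unstable angina requiring unplanned revascularization" or for heart failure. The word unplanned qualifies only the unstable-angina component. The section expects about 25 events and says that this analysis in particular will be limited.

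**Who can enter, and what the parent trial counts.** Inclusion criterion (b) admits patients with "Documented past history of MI OR past evidence of multivessel CAD by angiography". Section I says: "The CIRT primary endpoint is a composite of nonfatal myocardial infarction (MI), stroke, and cardiovascular death". Coronary revascularization is among the parent trial's secondary endpoints, also without qualifier.

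**The concern.** Section II says that "CFR provides a robust and reproducible clinical measure of the integrated hemodynamic effects of epicardial CAD", together with diffuse and microvascular disease. A patient whose study scan shows ischemia will therefore tend to have a low CFR. If a site investigator sees that ischemia and a revascularization follows, the model records an event in a low-CFR patient that happened because the scan was done. That is work-up bias: the predictor's own measurement generates part of the outcome. It could make CFR level look prognostic when it is not.

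The MI component raises a separate definitional question. Read literally, a first nonfatal MI in a patient who entered on multivessel CAD with no prior MI is not an event, although the parent primary endpoint would count it. This has nothing to do with scans, but it sits in the same sentence.

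At stake is the plan's only analysis that links CFR to clinical events, in a trial that presents validation of CFR as an imaging biomarker as one of its purposes. No randomized comparison and no primary or secondary endpoint is affected.

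**Working it through.** **1. Is the route open?** Site investigators review every scan (section V). Any coronary revascularization counts as an event (section VI). No text excludes, flags or separately reports a procedure prompted by a scan, and no sensitivity analysis is planned. The core laboratory's results are withheld, but the site reads its own images. Section IV makes BWH both the Core Imaging Lab and the imaging center for four of the six clinical sites, and no separation of readers is described. The route is open. Whether anyone takes it is not stated.

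**2. How many events could be affected?** The figure of about 25 cannot be reproduced, because no rates are given for the components. As a consistency check, use the parent planning figures in section I (530 primary events, 7,000 patients, 3 years on average) and the 150 patients in section IV:

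- 530/7,000 = 7.57%; 150 × 0.0757 = 11.4 events at about 3 years.
- Scaled to 4 years, since objective (1) refers to 3–4 years: 11.4 × 4/3 = 15.1.
- Left for the other components: 25 − 11.4 = 13.6 (55%), or 25 − 15.1 = 9.9 (39%).

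Those other components are revascularization, unstable angina, heart failure and non-cardiovascular death together. The share that is revascularization is not given, and still less the share prompted by a scan.

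**3. CFR level, median split.** Assume 75 patients in each half, no true effect of CFR, and k of 25 events prompted by a scan, all in the low-CFR half. Then low = (25 − k)/2 + k, high = (25 − k)/2, HR = ln(1 − low/75)/ln(1 − high/75), and P(p<0.05) ≈ Φ(ln HR × √(25/4) − 1.96).

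For k = 5: low 15, high 10; HR = ln(0.800)/ln(0.867) = 1.56; Φ(0.444 × 2.5 − 1.96) = Φ(−0.85) = 0.20.

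| k | HR | P(p<0.05) |
|---|---|---|
| 1 | 1.09 | 4% |
| 2 | 1.19 | 6% |
| 3 | 1.30 | 10% |
| 5 | 1.56 | 20% |
| 8 | 2.07 | 44% |

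The formula counts one tail only, so k = 1 falls just under 5%. The split also matches exactly how the extra events were assigned, which makes the effect large.

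**4. CFR level, continuous.** A Cox model on continuous CFR is closer to the plan. It was simulated with 150 patients, about 25 events and no true effect, in separate runs of 600, 1,200 and 1,500 replicates:

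| Scan-prompted events | All in low-CFR half | 75% in low-CFR half |
|---|---|---|
| 0 | 4–6% | – |
| 1 or 2 | about 5% | – |
| 4 | 8–10% | 6% |
| 6 | 15–18% | 6% |
| 8 | 23–28% | 9% |

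The 75% column comes from the 1,200-replicate run only. All counts and allocations are assumptions.

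**5. Change in CFR.** These calculations use a single CFR level. For change, the sign is unclear. A procedure prompted by the baseline scan comes before the follow-up scan and could raise CFR, which pairs an event with improvement. One prompted by a poor follow-up scan would pair an event with decline.

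**6. First MI.** Inclusion criterion (b) joins prior MI and multivessel CAD by OR, so a patient may enter with no prior MI. The composite lists MI only as recurrent; the parent primary endpoint lists nonfatal MI without that limit. No arithmetic is needed: on a literal reading the two endpoints differ for these patients.

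**The case against.** The strongest reply is that the causal chain is not in the documents. The review is for safety, the scans are for research, they are not assessed in real time, and the core laboratory returns nothing. No sentence says that a finding reaches a treating physician or leads to a procedure. This stands, and it limits the conclusion to a possibility. It does not close the route, because the site review takes place despite those restrictions.

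Second, the composite is essentially the parent primary endpoint plus parent secondary endpoints, so unqualified revascularization follows the parent trial. This stands as to its origin. But the parent compares randomized arms, whereas here the scan result itself is the predictor. The appendix with the parent protocol summary was not in the text available, so its event definitions could not be checked.

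Third, 4 to 8 scan-prompted events, all in low-CFR patients, is a worst case. It would be 29% to 57% of about 14 other-component events (4/14 and 8/14). With three quarters of them in the lower half, rejection stays at 6–9%. This stands.

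Fourth, the MI wording is probably loose drafting in a CAD population. That may be so, but a literal reading would still miscount.

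Finally, the analysis is exploratory, and the plan says that the study is not powered for clinical outcomes. This stands and sets the severity.

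**Conclusion.** This is a minor point that is cheap to repair. The plan allows a revascularization prompted by a study scan to be scored as an event predicted by that scan, so the association of CFR level with MACE can be inflated. One or two such procedures among about 25 events would not matter. Several, concentrated in low-CFR patients, would. This rests on three assumptions: that some site findings lead to procedures, how many do, and where they fall on the CFR scale. The documents settle none of them.

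A reader might infer that the study scans will cause the outcome, that the CFR–MACE association is inflated, or that the bias extends to change in CFR. The documents support none of these: no acting on findings is described, no count is given, and the direction for change is not established. Nor does the MI wording bear on work-up bias. It is a separate defect, and it holds on a literal reading.

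**What to change.** In section VI, Exploratory analyses, objective (1):

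- Replace recurrent MI with nonfatal MI, as in the parent primary endpoint.
- Keep the planned composite, and report the same proportional hazards model as a sensitivity analysis either without coronary revascularization or for the parent endpoint of nonfatal MI, stroke and cardiovascular death.
- Where the reason for a procedure is recorded, list revascularizations prompted by a study scan separately. The documents describe no such record, so this depends on what the sites hold.

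Excluding elective procedures within a fixed window after a scan is not advised. Any window would be arbitrary and would also drop procedures unrelated to the scan.

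The cost is a wording change and one extra model with fewer events: about 11 at 3 years to 15 at 4 years for the parent endpoint, instead of about 25. On a median split, the hazard ratio detectable with 80% power is exp[(1.96 + 0.84)/√(d/4)] for d events. It rises from about 3.1 (25 events) to 4.2 (15) or 5.4 (11). The sensitivity model will therefore have a wide interval. It can show whether the estimate depends on revascularization, but it cannot settle whether CFR is prognostic.

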## VI. BIOSTATISTICAL ANALYSIS

CIRT-CFR sites participating in the proposed ancillary study. Based on our power analysis and sample size calculations, we estimate that each of the 6 clinical sites will be required to enroll approximately 25 patients over approximately 3 years. This is equivalent to 1 patient every 6 weeks per site, which we believe is reasonable and attainable. All sites have received IRB approval for the parent study and are actively enrolling patients in the parent CIRT trial. The proposed imaging studies (PET scans and echos) are routinely performed at the 3 imaging sites (BWH, OHI, and UAB). Drs. [name] (PI) and [name] (both at BWH), [name] (OHI), and [name] (UAB) are recognized experts in quantitative PET imaging and echocardiography, have published widely on these topics, and have extensive experience in conducting clinical trials using imaging endpoints.

***Aim 1. To test the hypothesis that systemic inflammation is a critical determinant of coronary flow reserve (CFR) and myocardial tissue perfusion, as assessed by quantitative PET imaging, in stable CAD patients with type 2 DM or metabolic syndrome.*** Specifically, we propose that treatment with LDM at a target dose of 15 to 20 mg orally weekly for 1-12 months will, compared to placebo, result in:

***Hypothesis #1:*** Improved global CFR in response to dipyridamole, reflecting primarily endothelium-independent vasodilation.

***Hypothesis #2:*** Reduced total stress perfusion deficit, a semi-quantitative score combining scar and ischemia.

**Methods:** PET scans will be performed at the 3 imaging sites at randomization and at 1-12-month follow-up using a standardized study protocol. As described in section V, we have previously demonstrated feasibility of measuring myocardial blood flow with high reproducibility. In addition to CFR and coronary hemodynamics, we will also measure the total perfusion deficit (TPD) during stress and at rest, and calculate the difference TPD between stress and rest (reflecting total ischemic burden) using previously validated methods. The primary endpoint for the efficacy portion of *Aim 1* is the change in global CFR response to dipyridamole, reflecting primarily endothelium-independent coronary vasodilatation, over 1-12 months. A key secondary endpoint is the change in dipyridamole-stimulated TPDstress, reflecting the combined extent and severity of ischemia and scar, over 1-12 months. Tertiary endpoints include the change in hyperemic global and regional (i.e., non-infarcted myocardium)

myocardial blood flow (MBF), and the change in global and regional TPDstress-rest (reflecting the ischemia score) over 1-12 months.

**Statistical analyses:** For the analyses of both primary and secondary endpoints included in *Hypotheses 1 and 2*, we will use separate linear regression models with the respective change in global CFR (in response to dipyridamole) and TPDstress over 1-12 months as the outcome variables. Each of these regression models will control for baseline variables of stratum (DM or metabolic syndrome), time since index MI (< 6 months or ≥6 months), imaging site (BWH or OHI), the corresponding baseline global CFR score, as well as treatment assignment. Although we expect the distribution of change scores to be approximately normal, preliminary analyses will evaluate whether a transformation from the Box-Cox family will improve that assumption. From our experience in prior clinical trials using a similar design to CIRT-CFR, we expect a 10-15% attrition rate of patients due to death or loss to follow-up. Because it is not expected that site randomization assignment will influence these events, and because the available information is unlikely to allow for accurate imputation of missing values for CFR, subjects who do not have a repeat 1-12-month PET scan will not be included in the primary or secondary analyses.

**Power calculations:** For *Aim 1*, we used prior publications from our group to characterize the reproducibility of the global, dipyridamole mediated CFR measurements in patients with DM or metabolic syndrome. We used data from the patients enrolled in the placebo arm of these trials to estimate the standard deviation in the change in global CFR (Time 2 CFR – Time 1 CFR), and found a mean standard deviation of 0.45. **Table 1** shows the sample size needed to reach 80-90% power for an expected effect size of 20% relative improvement in CFR in the active treatment group compared to placebo. Using a total sample size of 130 evaluable patients and a two-tailed alpha of 0.05, power will be 85% for this analysis. Estimated power by this approach should be considered conservative since the control for baseline CFR is expected to enhance power. ***We expect to randomize approximately 150 patients*** to have at least 130 evaluable subjects completing the study (estimating a 10-15% attrition rate between time of randomization and final PET).

**Table 1.** Power and sample size calculations for Aim 1

AIM 1 Measurement	Difference (LDM vs. placebo)	Standard deviation (placebo)	Two-sided α level	Total sample size for power		
				80%	85%	90%
Primary outcome:						
ΔCFR to dipyridamole	0.24	0.45	0.05	114	130	150
Secondary outcome:						
ΔTPD stress	2.5%	4.9%	0.05	124	140	164

***Aim 2. To test the hypothesis that LDM at a target dose of 15 to 20 mg orally weekly for 1-12 months will, compared to placebo, result in improved LV myocardial mechanics, as assessed by transthoracic echocardiography, and that this functional improvement will correlate with the change in CFR after 1-12 months of treatment.*** Specifically:

***Hypothesis #3:*** LDM for 1-12 months will result in improved LV systolic function, as assessed by measures of LV peak global longitudinal strain, and diastolic function, as assessed by measures of tissue Doppler mitral annular early diastolic relaxation velocity (E’).

**Hypothesis #4:** Changes in LV systolic and diastolic function after 1-12 months of LDM therapy will be correlated with changes in coronary flow reserve.

**Methods:** 2-D echocardiograms will be performed at the 3 enrolling imaging sites at baseline and 12 months after randomization in accordance with standard clinical practice and utilizing a standardized study protocol as outlined in section V. As described in section V, we have previously demonstrated feasibility of measuring cardiac mechanics with high reproducibility. The primary efficacy endpoints for *Aim 2* are the change in LV peak global longitudinal strain (GLS) (systolic function) and in tissue Doppler mitral annular early diastolic relaxation velocity (E') (diastolic function). Key secondary endpoints are change in other LV systolic function measures (LVEF and tissue Doppler peak systolic mitral annular velocity (S')), as well as change in other LV diastolic function measures (LV early diastolic strain rate by speckle-tracking, and mitral inflow Doppler E velocity to E' ratio (E/E')). Tertiary endpoints include changes in more conventional measures of LV structure (e.g. volumes, wall thickness, mass) over 1-12 months.

**Statistical analyses. Hypothesis 3:** We will use separate linear regression models with the respective change in LV peak GLS and E' over 1-12 months as the outcome variables. Each of these regression models will control for baseline variables of stratum (DM or metabolic syndrome), time since index MI (< 6 months or ≥ 6 months), imaging site (BWH, OHI, or UAB), the corresponding baseline LV peak GLS and E' scores, as well as treatment assignment.

**Hypothesis 4:** Although temporality cannot be established in correlational analysis of concurrent changes, we will also use regression models to clarify the association of changes in CFR and LV function. Controlling for treatment assignment, baseline stratification variables, baseline CFR and LV function, as well as change in LV function, our outcome will be change in CFR. By adding the baseline and change in LV function to our primary model for *Aim 2*, we will explore whether changes in CFR are associated with changes in LV function, or whether independent treatment effects remain.

**Power calculations:** For *Aim 2*, we used prior publications from our team to characterize the reproducibility of the LV measures of systolic and diastolic function. Power analysis is based upon the following assumptions: the expected effect size is 10% relative improvement in each of the primary and secondary outcome measures in the active treatment group compared to placebo. **Table 2** shows the sample size needed to reach 80-90% power for each of the primary and secondary efficacy measures. As for *Aim 1*, estimated power by this approach should be considered conservative since the control for baseline scores is expected to enhance power. Of the 150 patients we expect to randomize, there will be at least 130 evaluable subjects completing the study (estimating a 10-15% attrition rate between time of randomization and final echo).

**Table 2.** Power and sample size calculations for Aim 2

AIM 2 Measurement	Difference (LDM vs. placebo)	Standard deviation (placebo)	Two-sided $\alpha$ level	Total sample size for power		
				80%	85%	90%
Primary outcome:						
Systolic: $\Delta\text{GLS}_{\text{peak}}$	1.4%	2.8	0.05	126	142	166
Diastolic: $\Delta\text{E}'_{\text{velocity}}$	0.7 cm/s	1.3	0.05	112	126	148
Secondary outcomes:						
Systolic: $\Delta\text{S}'$	0.6 cm/s	1.2	0.05	128	146	172
$\Delta\text{LVEF}$	1.5%	3.1	0.05	138	156	182
Diastolic: $\Delta\text{E}/\text{E}'$	1.1	2.0	0.05	128	146	172
$\Delta\text{LAVI}$	1.2 ml/m 	2.3	0.05	118	134	158

**Exploratory analyses:** The proposed ancillary study will not be powered to detect changes in clinical outcomes, patient symptoms, or changes in circulating biomarkers. However, we recognize the importance of exploring the correlations between the changes in CFR and LV function over the 1-12-month observation period and these meaningful outcomes. We propose the following exploratory tertiary objectives: (1) Explore an interaction between the change in CFR at 1-12 months with composite MACE that includes cardiac and all-cause mortality, recurrent MI, stroke, coronary revascularization, and hospitalization for unstable angina requiring unplanned revascularization or for congestive heart failure, occurring 3-4 years after randomization. We will use a proportional hazards model to explore relationships of CFR and its change with time until development of the first clinical event occurring through the end of randomization. We recognize that this exploratory analysis, in particular, will be limited because we expect only ~25 composite events in total in our study sample. (2) Correlate the change in CFR at 1-12 months with the corresponding change in QOL scores, as assessed by the standardized SF-36 Health Survey to be administered during enrollment, 12-month, and final study visits of the parent CIRT trial. Prior assessments with this tool have shown significant differences in baseline and 6-month follow-up scores in a modest-sized (n=120) patient population post-MI. (3) Correlate the change in CFR and LV function with the corresponding changes in circulating biomarkers of inflammation (hsCRP, IL-1) and myocardial strain (NTproBNP, hsTroponin), as assessed from stored biorepository samples at 8, 12 and 24 months after randomization. Analyses of changes in QOL scores and biomarkers will use linear regression models, after transforming changes to normality as necessary, and with control for baseline trial stratification variables, baseline QOL scores and biomarker levels, and treatment assignment. Main independent variables will be baseline and 1-12-month change in CFR. (4) Assess correlations among the baseline PET, echo, biomarker, and SF-36 data using linear regression models, as described above for continuous variables.

